7.5.2 Immunogenicity

Detection of ADAs against camidanlumab tesirine will be performed by using a screening assay for identification of antibody positive samples/patients, a confirmation assay, and titer assessment.

[figure not shown]
Up to 6 mL of whole blood will be collected as per [Table 1](#) and [Table 8](#) for the patients treated with camidanlumab tesirine as monotherapy, as per [Table 2](#) and [Table 9](#) for the patients treated with camidanlumab tesirine in combination with pembrolizumab.

[figure not shown]
Blood should be drawn from a vein away from the one used for study drug infusion.

[figure not shown]
For patients who test positive for ADA, additional ADA samples will be requested for testing every 12 weeks following the EOT visit until the ADA titer falls to a background level, as long as the patient is still on-study.

[figure not shown]
The ADA samples must be stored at $\leq -70^{\circ}\text{C}$. Please refer to the laboratory manual for detailed instructions regarding specimen handling and shipment.

For patients treated with camidanlumab tesirine in combination with pembrolizumab, unless there is a penultimate observation of positive ADA response, no other collection of ADA data is necessary if camindanlumab tesirine administration is discontinued.

8 ADVERSE EVENTS

8.1 Definition of Adverse Events, Serious Adverse Events, and Adverse Events of Special Interest

An AE is defined as any untoward medical occurrence in a patient or clinical investigation subject administered a pharmaceutical product, which does not necessarily have to have a causal relationship with this treatment.

Test results collected during the study (e.g., laboratory values, physical examinations, ECGs, etc.) or identified from review of other documents may constitute AEs if deemed clinically significant.

An SAE is defined as any AE that:

- results in death.
- is life threatening.
- requires inpatient hospitalization or prolongation of existing hospitalization (hospitalization for elective procedures or for protocol compliance is not considered an SAE).
- results in persistent or significant disability/incapacity.
- is a congenital anomaly/birth defect.
- important medical events that do not meet the preceding criteria but based on appropriate medical judgement may jeopardize the patient or may require medical or surgical intervention to prevent any of the outcomes listed above.

Adverse Events of Special Interest (AESIs) are significant AEs that are judged to be of special interest because of clinical importance, known class effects, or based on preclinical signals. Events considered to be AESIs are identified in Section [8.1.1](#).

8.1.1 Adverse Events of Special Interest

For this study the following AEs, irrespective of seriousness and causality, are considered AESIs (except those clearly attributed to pembrolizumab alone):

- GBS (including variants such as acute motor and sensory axonal neuropathy)
- Polyradiculopathy
- Autonomic nervous system imbalance
- Nerve palsy
- \geq Grade 3 neurologic toxicities
- \geq Grade 3 immune-mediated toxicities. Of note, rashes will not be considered as immune-mediated skin toxicities, since they are well described toxicities of PBD-dimers; with exception for Stevens-Johnson syndrome, toxic epidermal necrolysis, acute generalized exanthematous pustulosis, exfoliative dermatitis, and drug reaction with eosinophilia and systemic symptoms (Note: immune-mediated skin toxicities will need confirmatory skin biopsy)

- Autoimmune-mediated events (such as, but not limited to, pneumonitis, hepatitis, colitis, endocrinopathies, type 1 diabetes mellitus, and nephritis/renal dysfunction)

For all AESIs it is important to provide as much information as possible: e.g., time of onset (including changes in severity), duration of events, time to resolution, and relationship to camidanlumab tesirine. It is also important to specify if any AEs are autoimmune mediated.

Adverse events of special interest will be closely monitored and followed.

8.2 Eliciting and Reporting Adverse Events/Adverse Events of Special Interest/Serious Adverse Events

Patients will be instructed to contact the Investigator at any time after ICF signature if any symptoms develop. At each study visit, patients will be asked a non-leading question to elicit any medically related changes in their well-being. Patients may also report AEs voluntarily and they will be instructed to contact the Investigator between visits if any symptoms develop or worsen.

All AEs will be reported starting when the patient provides written informed consent. Clinically significant medical conditions present at the time of ICF signature will be reported as medical history. Clinically significant medical conditions that start or worsen after ICF signature will be reported as AEs.

All AEs, AESIs, and SAEs, regardless of relationship to study drugs (camidanlumab tesirine and pembrolizumab), will be reported from the time the patient signs the ICF until 30 days after the last dose of study drug; thereafter, only related SAEs will be reported.

Whenever possible, AEs should be reported as a diagnosis rather than individual signs and symptoms. If no diagnosis is available or has been identified, then the primary symptom is reported.

In general, the term ‘disease progression’ should not be used for reporting an AE/SAE. However, AEs/SAEs that are complications of disease progression should be reported.

All AEs reported or observed during the study will be recorded on the AE page of the eCRF. Information to be collected will include event term, date of onset, assessment of severity (Section 8.3), seriousness (Section 8.1), relationship to study drug (Section 8.4), action taken with study drug, date of resolution of the event or ongoing (when no resolution by the end of the reporting period), any required treatment or evaluations, and outcome.

New serious AESIs/SAEs and any recurrent episodes, progression, or complications of the original serious AESI/SAE must be reported to the pharmacovigilance department of the Sponsor or delegate (e.g., contract research organization [CRO]) within 24 hours after the time site personnel first learn about the event. Reporting will occur through the electronic data capture (EDC) system.

Any recurrence of GBS/polyradiculopathy, irrespective of the relationship to study drug, has to be reported to the Sponsor, including when the recurrence occurs when the patient has already completed the study. The reporting of such events after the patient has completed the study will be captured via the Sponsor’s safety database and therefore will not impact database lock.

Non-serious AESIs must be entered in the EDC system and reported to the Sponsor or delegate (e.g., CRO) within 48 hours after the time site personnel first learn about the event.

8.3 Assessment of Severity

All AEs will be graded according to CTCAE version 4.0. For events not included in the CTCAE criteria, the severity of the AE is graded on a scale of 1 to 5 as shown in [Table 12](#).

Table 12. Definition of Severity Grades for Common Terminology Criteria for Adverse Events

Grade	Definition
1	Mild; asymptomatic or mild symptoms; clinical or diagnostic observations only; intervention not indicated.
2	Moderate; minimal, local, or noninvasive intervention indicated; limiting age appropriate instrumental activities of daily living (ADL) ^a .
3	Severe or medically significant but not immediately life threatening; hospitalization or prolongation of hospitalization indicated; disabling; limiting self-care ADL. ^b
4	Life-threatening consequences; urgent intervention indicated.
5	Death related to adverse event.

^a ADL refers to preparing meals, shopping for groceries or clothes, using the telephone, managing money, etc.

^b Self-care ADL refers to bathing, dressing and undressing, feeding self, using the toilet, taking medications, and not bedridden.

The AEs characterized as intermittent do not require documentation of onset and duration of each episode.

8.4 Assessment of Causality

The Investigator's assessment of an AE's relationship to study drug is an important part of safety reporting but is not a factor in determining whether an AE is reported. An AE will be assessed as related to study drug if there is a reasonable possibility of causal relationship with the use of the study drug. For SAEs, whenever possible, the Investigator should provide a rationale for the causality assessment.

8.5 Regulatory Reporting

Reporting of AEs to competent authorities and independent ethics committees (IECs) will be consistent with local laws, regulations, guidelines, and requests.

8.6 Pregnancy Reporting

Any pregnancy in a participant that occurs from signing the ICF up to 9.5 months after the last dose of camidanlumab tesirine, or up to 4 months after the last dose of pembrolizumab, whichever is the latest, must be reported using the Pregnancy Report Form. Any pregnancy in a partner of a male patient that occurs from signing the ICF up to 6.5 months after the last dose of camidanlumab tesirine, or up to 4 months after the last dose of pembrolizumab, whichever is the latest, must be reported. Pregnancy must be reported within 24 hours after the site personnel first learn of the pregnancy. The pregnancy itself is not considered an AE. However, the pregnancy must be followed to determine outcome (including spontaneous

miscarriage, elective termination, normal birth, or congenital abnormality) and status of mother and child, even if the patient discontinued from the study. Abortions (elective or spontaneous) must be reported as an SAE.

Any SAE occurring in association with a pregnancy that is brought to the Investigator's attention after the patient has completed the study and considered by the Investigator as possibly related to the study drug must be promptly reported in the same manner.

Once pregnancy is confirmed in a study participant, study drug will be discontinued; see Section [7.4.6](#) for additional information.

9 STATISTICAL CONSIDERATIONS

Full details of the analysis plan, including a more technical and detailed elaboration of the statistical analyses, will be provided in the statistical analysis plan (SAP). [REDACTED]

9.1 Sample Size Calculation

Approximately 95 patients; Part 1 may enroll approximately 65 patients and Part 2 will enroll approximately 30 patients, approximately 16 patients in Group 1 and 14 in Group 2.

9.2 Analysis Populations

- The Safety analysis set consists of all patients who receive study drug
- The DLT-evaluable analysis set consists of patients in Part 1 who receive study drug: However, this set excludes:
 - Patients in Part 1 who discontinue from the study during the DLT period (see Section 6.5) without experiencing a DLT
 - Patients in Part 1 enrolled in the paired-biopsy cohort
 - Additional patients in Part 1, of same indication, enrolled at a dose level equal or higher to the dose level for which at least 1 patient with documented PR or CR has been observed
- The Efficacy analysis set will consist of all patients who receive at least 1 dose of study drug (refer to Section 6), have valid Baseline disease assessment(s), and at least one valid post-Baseline disease assessment. Patients who do not have a post-Baseline assessment due to early clinical progression or death (after receiving study drug) will also be included.
- The PK analysis set consists of all patients who receive study drug and have at least 1 pre-(C1D1) and 1 post-dose valid assessment.

9.3 Interim Analysis

No formal interim analysis is planned.

9.4 Final Analysis

All efficacy and safety endpoints will be analyzed and reported in the clinical study report (CSR).

9.5 Demographics and Baseline Characteristics

Demographics and Baseline characteristics, such as cancer history and medications history, will be summarized for the Safety analysis set by dose level.

9.6 Exposure to Treatments

Exposure to study drug, prior, and concomitant medications will be summarized for the Safety analysis set by dose level. Dose interruptions, reductions, and relative dose intensity will also be summarized.

9.7 Efficacy Analyses

9.7.1 Overall Response Rate

The ORR by RECIST v 1.1 will be defined as the proportion of patients with a best overall response (BOR) of CR or PR. The overall response category will be derived based on response assessment performed on or before the start of subsequent anti-cancer therapy.

The percentage of ORR with its 95% confidence interval (CI) will be presented. In contrast to CR, PR, or PD, a BOR of SD can only be made after the patient is on-study for a minimum of 35 days after the first dose of study drug. Any tumor assessment indicating SD before this time period will be considered as a non-evaluable for BOR if no assessment after this time period is available.

9.7.2 Duration of Response

Duration of response by RECIST 1.1 will be defined among responders (CR or PR) as the time from the earliest date of first response until the first date of either disease progression or death due to any cause.

The date of disease progression will be defined as the earliest date of disease progression. For patients who have not progressed or died at the time of the analysis, censoring will be performed using the date of the last valid disease assessment. The data will be analyzed by the Kaplan-Meier method for all responders and by response (CR/PR). The median duration of response and 95% CI will be presented. Further details will be outlined in the SAP.

9.7.3 Progression-Free Survival

PFS will be defined as the time from first dose of study drug until the first date of either disease progression or death due to any cause. The date of disease progression will be defined as the earliest date of disease progression. For patients whose disease has not progressed at the time of the analysis, censoring will be performed using the date of the last valid disease assessment. The data will be analyzed by the Kaplan-Meier method. The median PFS time and 95% CI will be presented. Further details will be outlined in the SAP.

9.7.4 Overall Survival

Median OS will be defined as the time from the first dose of study drug until death due to any cause. For patients who have not died at the time of the analysis, censoring will be performed using the date the patient was last known to be alive. The data will be analyzed by the Kaplan-Meier method. The median OS and 95% CI will be presented. Further details will be outlined in the SAP.

9.8 Safety Analyses

Safety analyses will be presented descriptively.

9.8.1 Adverse Events

The focus of AE summarization will be on TEAEs. A TEAE is defined as an AE that occurs or worsens in the period extending from the first dose of study drug to 30 days after the last dose of study drug in this study or start of a new anticancer therapy, whichever is earlier.

All TEAEs will be summarized. Summary tables will be presented to show the number of patients reporting TEAEs by severity grade and corresponding percentages. A patient who reports multiple TEAEs within the same Preferred Term (or System Organ Class) is counted only once for that Preferred Term (or System Organ Class) using the worst severity grade.

Separate summaries will be prepared for TEAEs classified as severe or life-threatening (\geq Grade 3); study drug-related AEs; AEs leading to treatment interruption, modification, or discontinuation; AESIs; SAEs; and death.

9.8.2 Clinical Laboratory Results

Clinical hematology, coagulation panel, biochemistry, and urinalysis data will be summarized at each scheduled assessment. Shifts for clinical laboratory results that can be graded according to CTCAE version 4.0 will be summarized by CTCAE grade. Shifts for other numeric laboratory results will be by high/normal/low flag. Shifts for all other laboratory results will be by normal/abnormal flag.

Summaries by visit will include data from scheduled assessments, and all data will be reported according to the nominal visit date for which it was recorded. Unscheduled data will be included in “worst-case post-Baseline” summaries, which will capture a worst case across all scheduled and unscheduled visits after the first dose of study drug. Further details will be provided in the SAP.

[figure not shown]
9.8.3 Additional Safety Assessments

The results of scheduled assessments of vital signs, physical examinations, ECOG performance status, and 12-lead ECGs will be summarized. All data will be reported according to the nominal visit date for which it was recorded (i.e., no visit windows will be applied). Unscheduled data will be included in “worst case” summaries, which will capture a worst case across all scheduled and unscheduled visits after the first dose of study drug. All data will be listed. Further details will be provided in the SAP.

9.9 Pharmacokinetic Analyses

The PK profile will include determination of: maximum concentration (C_{max}), time to C_{max} (T_{max}), area under the concentration-time curve from time zero to the last quantifiable concentration (AUC_{last}), area under the concentration-time curve from time zero to the end of the dosing interval (AUC_{tau}), area under the concentration-time curve from time zero to infinity (AUC_{inf}), apparent terminal elimination half-life (T_{half}), CL, volume of distribution (V_d), and accumulation index (AI).

Pharmacokinetic parameters will be determined for all PK-evaluable patients using a non-compartmental method with Phoenix WinNonlin (Certara USA, Inc., Princeton, NJ, US) or other appropriate software. Results will be reported as part of the CSR. Supplemental analysis may be performed, as appropriate, by integrating with data from other camidanlumab tesirine studies, and would be reported separately.

9.10 Immunogenicity Analyses

A tiered immunogenicity strategy (Figure 3) will be undertaken to evaluate ADAs by screening and confirmatory assays with titer evaluation, followed by characterization and evaluation of neutralizing capacity as needed. ADA sample collection, banking, and testing in validated and to be validated assays will be according to the new FDA Draft Guidance for Industry (April 2016): ‘Assay Development and Validation for Immunogenicity testing of Therapeutic Protein Products’

[figure not shown]

Figure 3. Anti-drug Antibody Tiered Immunogenicity Testing Strategy

Abbreviations: ADA=anti-drug antibody; ADC=antibody-drug conjugate; BSA=bovine serum albumin; mAb=monoclonal antibody; PK=pharmacokinetics.

Results from ADA testing will include tabular summarization for number/proportion of patients with positive pre-dose ADA response, number of patients with post-dose ADA response only, and number of patients with positive ADA response at any time. The denominator will be the total number of patients tested for ADAs in the study. For patients exhibiting a positive ADA, PK, safety and efficacy correlates will be assessed and reported.

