1.3.4 ADCT-301-103

As of 14 April 2021, enrolment in the monotherapy part was completed; 44 patients were treated with camidanlumab tesirine monotherapy in Part 1 at 8 dose levels ranging from 20 to 150 $\mu\text{g}/\text{kg}$ administered on a 3-week treatment cycle and the MTD has not been reached.

The most frequently reported TEAEs ($\geq 20\%$ overall), regardless of grade or relationship, included: nausea (40.9%), fatigue and decreased appetite (36.4% each), constipation (29.5%), abdominal pain (27.3%), rash (22.7%). ([Puzanov, 2021](#)).

The TEAEs that have been assessed as Grade ≥ 3 were reported in 31 out of 44 (70.5%) patients. The most common Grade ≥ 3 TEAEs (observed in at least 5% of patients overall), regardless of relationship, included anemia (11.4%), abdominal pain, rash and pulmonary embolism (6.8% each).

Grade 3 autoimmune AE (colitis, immune-mediated adverse event, systemic inflammatory response syndrome) and grade 3 neurologic AE (dysphagia and asthenia), regardless of relationship, were observed in 6.8% and 4.5% of the patients, respectively.

Best overall responses were stable disease (SD) for 11 patients (25%) and progressive disease (PD) for 23 patients (52.3%); 2 patients were not evaluable (4.4%) and 8 (18.2%) had no post-baseline evaluation due to death (11.4%) or clinical progression (6.8%).

Some patients with paired biopsies showed decreased Tregs and increased Teffs:Tregs ratio in the local tumor environment, supporting a therapeutic rationale for the treatment of advanced solid tumors with camidanlumab tesirine in combination with other immune-modulating therapies ([Puzanov, 2020](#)).

At the time of this Protocol Amendment 7, the study is enrolling patients receiving camidanlumab tesirine in combination with pembrolizumab.

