Evaluate the preliminary anti-tumor activity of camidanlumab tesirine as monotherapy and camidanlumab tesirine in combination with pembrolizumab	
Overall response rate (ORR) according to the Response Evaluation Criteria In Solid Tumors (RECIST) v1.1, for patients treated with camidanlumab tesirine as monotherapy and for patients treated with camidanlumab tesirine in combination with pembrolizumabDuration of response (DOR) defined as the time from the first documentation of tumor response to disease progression as per RECIST v 1.1, or death for patients treated with camidanlumab tesirine as monotherapy and for patients treated with camidanlumab tesirine in combination with pembrolizumabProgression-free survival (PFS) defined as the time between start of treatment and the first documentation of recurrence, progression, as per RECIST v 1.1, or death for patients treated with camidanlumab tesirine as monotherapy and for patients treated with camidanlumab tesirine in combination with pembrolizumabOverall survival (OS) defined as the time between the start of treatment and death from any cause for patients treated with camidanlumab tesirine as monotherapy and for patients treated with camidanlumab tesirine in combination with pembrolizumab

Objectives	Endpoints
Evaluate the pharmacokinetic (PK) profile of camidanlumab tesirine as monotherapy and camidanlumab tesirine in combination with pembrolizumab	
Concentrations and PK parameters of camidanlumab tesirine total antibody, PBD-conjugated antibody, and unconjugated warhead SG3199 in serum
Evaluate the immunogenicity of camidanlumab tesirine as monotherapy and camidanlumab tesirine in combination with pembrolizumab	
Frequency of confirmed positive anti-drug antibody (ADA) responses, their associated titers and, if applicable, neutralizing activity to camidanlumab tesirine after treatment with camidanlumab tesirine

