7.5.1 Pharmacokinetics

The PK profile of camidanlumab tesirine PBD-conjugated antibody, total antibody, and unconjugated warhead SG3199 will be assessed in serum by a central laboratory designated by the Sponsor using validated bioanalytical methods.

Up to 6 mL of whole blood will be collected as per [Table 1](#) and [Table 8](#) for the patients treated with camidanlumab tesirine as monotherapy, as per [Table 2](#) and [Table 9](#) for the patients treated with camidanlumab tesirine in combination with pembrolizumab.

Blood should be drawn from a vein away from the one used for study drug infusion.

The serum PK samples must be stored at $\leq -70^{\circ}\text{C}$. Please refer to the laboratory manual for detailed instructions regarding specimen handling and shipment.

At timepoints coinciding with ECG collection, PK blood collection should occur immediately after the end of the ECG recording and, when applicable, after vital signs (example in [Figure 2](#)). If a patient experiences Torsade de Pointes, concomitant PK samples (e.g., unscheduled) should be collected.

Table 8. Sampling Schedule for PK and ADA (Q3W Schedule): Camidanlumab Tesirine as Monotherapy

Cycle	Day	PK timepoint (window)	ADA timepoint (window)
C1	D1	Pre-dose (preferably within 2 h prior to start of infusion of camidanlumab tesirine) EOI of camidanlumab tesirine (-5 to +10 min) Post-dose* 4 h (\pm 10 min)	Pre-dose (preferably within 2 h prior to start of infusion of camidanlumab tesirine)
	D3	Post-dose* 48 h (\pm 24 h)	-
	D5	Post-dose* 96 h (\pm 24 h)	-
	D8	Post-dose* 168 h (\pm 48 h)	-
	D15	Post-dose* 336 h (\pm 48 h)	Post-dose* 336 h (\pm 48 h)
C2	D1	Pre-dose (within 2 h prior to start of infusion of camidanlumab tesirine) EOI of camidanlumab tesirine (-5 to +10 min) Post-dose* 4 h (\pm 10 min)	Pre-dose (within 2 h prior to start of infusion of camidanlumab tesirine)
	D3	Post-dose* 48 h (\pm 24 h)	-
	D5	Post-dose* 96 h (\pm 24 h)	-
	D8	Post-dose* 168 h (\pm 48 h)	-
	D15	Post-dose* 336 h (\pm 48 h)	-
C3 and C4	D1	Pre-dose (within 2 h prior to start of infusion of camidanlumab tesirine) Post-dose* 4 h (\pm 10 min)	Pre-dose (within 2 h prior to start of infusion of camidanlumab tesirine)
C5, C6, C7, every cycle	D1	Pre-dose (within 2 h prior to start of infusion of camidanlumab tesirine)	
C5, C7, every other cycle	D1		Pre-dose (within 2 h prior to start of infusion of camidanlumab tesirine)
EOT		At any time during visit day	At any time during visit day

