4.1.4 Pharmacokinetics (PK) Analysis Set

All patients who receive study drugs and have at least 1 pre-(C1D1) and 1 post-dose valid PK assessment.

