4.9.7 Pregnancy Test

Listing of pregnancy test results, if applicable, will be provided.

5 Final Analysis

All efficacy and safety endpoints will be analyzed and reported in the clinical study report (CSR). Results of PK analysis, immunogenicity analysis, [REDACTED] will be reported separately.

6 Data handling conventions

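### The post-dose-only ADA rate is divided by all patients tested for ADAs, including some who cannot meet its definition, so it can be understated

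*Protocol*

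**What the plan says.** Protocol section 3 (Table 3) lists as a secondary endpoint: "Frequency of confirmed positive anti-drug antibody (ADA) responses, their associated titers and, if applicable, neutralizing activity to camidanlumab tesirine after treatment with camidanlumab tesirine".

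Protocol section 9.10 plans three rows: patients positive before dosing, then "number of patients with post-dose ADA response only, and number of patients with positive ADA response at any time". It closes with one denominator: "The denominator will be the total number of patients tested for ADAs in the study". No post-dose sample is required for a patient to count as tested.

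Protocol Tables 8 and 9 (section 7.5.1) schedule an ADA sample before the first infusion for every patient, on monotherapy or combination. The first scheduled post-dose sample is Cycle 1 Day 15. Next come Cycle 2 Day 1 (pre-dose), later cycles, and an end-of-treatment (EOT) sample timed "At any time during visit day".

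Neither Protocol section 9.2 nor SAP section 4.1 defines an ADA-evaluable set. The PK set in SAP section 4.1.4, by contrast, is limited to patients who "have at least 1 pre-(C1D1) and 1 post-dose valid PK assessment". SAP section 3.3 records no modification to the protocol's statistical section. SAP section 5 defers "Results of PK analysis, immunogenicity analysis" and other results to separate reporting, without giving a denominator.

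**The concern.** The post-dose-only row comes closest to the stated endpoint, ADA arising after treatment. Two groups of tested patients cannot enter its numerator:

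- **Baseline-only patients.** Someone who gives the Cycle 1 Day 1 sample, leaves before Day 15 and has no EOT sample has been tested, but provides no post-dose information. The rule counts that patient as a non-event.
- **Baseline-positive patients.** The row's definition excludes them, yet they stay in its denominator, even when every patient has a post-dose sample.

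Both push the percentage down. If early loss differs between dose levels, or between monotherapy and combination, the dilution would differ too and would blur any comparison of ADA rates.

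**Working it through.** **No plan figure to reproduce.** The documents give no ADA rate, no baseline-positive share and no baseline-only share. The one related figure is in Protocol section 1.3.4: of 44 monotherapy patients, 8 had no post-baseline evaluation, through death (11.4%) or clinical progression (6.8%). As a check, 8/44 = 18.2%, 5/44 = 11.4% and 3/44 = 6.8%.

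**Formula.** Let N be the patients tested, b those with only a pre-dose sample, q those positive at baseline (each patient counted once), and x those negative at baseline and positive after dosing.

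- Reported rate = x / N
- Rate among patients who can qualify = x / (N - b - q)
- Ratio = (N - b - q) / N = 1 - f, with f = (b + q) / N

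Since f cannot be negative, the ratio never exceeds 1. It equals 1 only when both groups are empty.

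**Size, over assumed values of f:**

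| f | 1 - f | True 10% reads | True 20% reads |
|---|---|---|---|
| 0% | 1.00 | 10.0% | 20.0% |
| 2% | 0.98 | 9.8% | 19.6% |
| 5% | 0.95 | 9.5% | 19.0% |
| 10% | 0.90 | 9.0% | 18.0% |
| 18.2% | 0.818 | 8.2% | 16.4% |

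The true rates and the values of f are assumptions. Only the 18.2% comes from the documents, and there it describes tumour evaluation.

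**Both groups together.** With 10% baseline-only and, independently, 5% baseline-positive, the factor is 0.90 x 0.95 = 0.855, and a true 10% reads about 8.6%. With 18.2% baseline-only and 5% baseline-positive it is 0.818 x 0.95 = 0.777, and a true 10% reads about 7.8%. So the 18.2% limits the baseline-only part and not f as a whole.

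**In counts**, for the planned total of about 95 patients and no baseline-positives, with exact (Clopper-Pearson) 95% intervals:

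| Baseline-only | Positive | Rule in 9.10 | Restricted denominator |
|---|---|---|---|
| 5 | 9 | 9/95 = 9.5% (4.4 to 17.2) | 9/90 = 10.0% (4.7 to 18.1) |
| 17 | 8 | 8/95 = 8.4% (3.7 to 15.9) | 8/78 = 10.3% (4.5 to 19.2) |

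Even in the second case, the shift of about 2 points is small beside the width of the interval.

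**Why 18.2% is a ceiling.** The first scan is at week 6. To be baseline-only for ADA, a patient must miss the Day 15, Cycle 2 Day 1 and EOT samples. The 3 patients with clinical progression would have been asked to attend an EOT visit (Protocol section 5.4.1), where an ADA sample is scheduled. The documents do not say how many of the 5 deaths came before Day 15. The figure also covers monotherapy only, so applying it to the combination is a further assumption.

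**The case against.** Four points can be made for the plan.

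**The denominator suits the other rows.** Every patient with a baseline sample can be pre-dose positive, and a baseline-only patient can be positive at any time through that sample. This stands. A reader might infer that all three rows are biased, but the wording of section 9.10 does not support that; the clear defect is in the post-dose-only row.

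**One denominator makes the rows add up.** Pre-dose positives plus post-dose-only positives equal positives at any time, so over a common N the percentages add as well. This is a real convenience for a descriptive table. It does not make the middle percentage a rate among patients who could have had the event.

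**The sentence may not bind this row.** Section 9.10 uses the word proportion only for the pre-dose row and speaks of numbers for the other two. However, the denominator sentence is unrestricted and the endpoint is a frequency after treatment, so a percentage for the post-dose-only row is the natural reading.

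**The operative detail may lie elsewhere.** SAP section 5 sends immunogenicity to separate reporting, and a plan outside these documents may set a better rule. This lowers certainty about what will be reported. It does not cure section 9.10, the only rule the two documents contain.

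**Conclusion.** The point holds for the post-dose-only row. Its denominator includes patients who cannot meet the definition, and nothing in the protocol or SAP corrects this. Through the denominator, the rate can be understated and never overstated.

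The size is likely modest. It rests entirely on f, which the documents do not give and which may be near 0: for a true 10%, the loss is 0.2 points at f = 2%, 0.5 at 5% and 1.8 at 18.2%.

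Two stronger readings go too far. A reader might infer that immunogenicity will be understated; that follows only if baseline-only or baseline-positive patients exist, which the documents do not show. A reader might also take 18.2% as the share without a post-dose ADA sample; that figure concerns tumour evaluation, and ADA is sampled earlier and more often.

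No hypothesis is tested (SAP section 4), so no error rate or sample size depends on this. It is a worthwhile correction to a stated secondary endpoint.

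**What to change.** Replace the denominator sentence in Protocol section 9.10, or settle the matter in the separate immunogenicity analysis specification, with one denominator per row:

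- Pre-dose positive: all patients with a valid baseline ADA result.
- Post-dose only: patients negative at baseline with at least one valid post-dose ADA result.
- Positive at any time: all patients tested, as now.

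Show N for each row and the number of patients with no post-dose sample. Also state how a patient with a post-dose result but no valid baseline result is handled, since section 9.10 does not say; a separate count is enough.

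The cost is about one sentence, with no new samples or visits. The three percentages will no longer add up over one common N. The counts still will, provided any patients without a baseline result are shown separately. If every tested patient proves to be baseline-negative with a post-dose result, the post-dose-only percentage does not change.
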